2. Muscle of older adults contains fewer macrophages than muscle of younger adults. The number of macrophages that display markers of inflammation or anti-inflammation and growth increase for young but not older adults in response to exercise. Interestingly, macrophages that display the marker of anti-inflammation and growth outnumber macrophages displaying the marker of inflammation by approximately eight to one [2].
3. Muscle of older adults, compared to younger adults, has lower expression of genes associated with tissue growth and remodeling at rest and in response to a bout of resistance exercise [40].
4. Muscle gene expression associated with inflammation and growth is strongly correlated with muscle size and strength gained from training [3]. The number of macrophages in muscle is also correlated with size and strength gain, and gene expression suggesting that macrophage provision of cytokines, and growth and remodeling factors contributes to muscle adaptation to training.
5. The effects of aging on muscle macrophages are consistent with the immunosenescence of immune cells outside of muscle. For example, aging decreases the ability of peripheral blood mononuclear cells and T-cells to proliferate and respond to pro-inflammatory stimuli [1].
6. Pilot study findings suggest that the nutritional supplement can dampen systemic markers of inflammation and boost the antibody response to the pertussis antigen in older adults.

Finding 1: Muscle of older adults, as compared to young adults, has increased expression of cytokines at baseline and also lacks cytokine induction in response to acute resistance exercise [2].

Study: Pro- and anti-inflammatory cytokine mRNA levels were measured in muscle of young (22-41 yrs) and older (66-80 yrs) males (N=17 each) at rest and 72 hrs after completion of a single session of high-intensity resistance exercise targeting the thigh muscles. At rest, muscle of the older adults possessed higher (3.3-fold, $P=0.001$) the pro-inflammatory cytokine, IL1 β , than muscle from the younger adults (Figure 2A). Anti-inflammatory cytokines, IL1RA ($P=0.003$) and IL10 ($P=0.03$) were also higher in the old than young (not shown). After exercise, levels of the IL1 β increased (~2-fold, $P=0.006$) in the young muscle, but did not change in the old (Figure 2B). IL10 ($P=0.02$) also increased after exercise but only for the young subjects.

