- A. **Response to Vaccination:** β -hydroxy- β -methylbutyrate has been used in animal science to improve the response to vaccination [32]. The study will determine if 2-weeks of supplementation improves the response of older adults to the TDAP vaccine. The response to *pertussis* is of primary interest though the responses to the tetanus and diphtheria antigens will also be measured. Serum antibody titers will be compared between pre-vaccination and two time points post-vaccination. Enzyme-linked immunosorbent assays are available for measuring antibodies to each antigen (IBL International, Toronto, Ontario).
- B. **T-Cell Subpopulations:** Glutamine and arginine may be conditionally essential amino acids in the contexts of aging and exercise that are needed for optimal T-Cell function [34;56]. Aging decreases the ratio of naïve helper (CD4+) to cytotoxic (CD8+) T-Cells [57]; and though the levels of both cell populations increase shortly after moderate exercise for older adults, their levels do not reach the pre-exercise levels of young adults [58]. The proposed study will determine if 2-weeks of supplementation increases the CD4+ to CD8+ ratio or increases the response to acute exercise. A regulatory t-cell subset (CD4+, CD25+, FoxP3+) will also be examined since these cells function as regulators of immune function that prevent an uncontrolled immune response or autoimmunity [59]. Assessment of T-cell subsets will be carried out by flow cytometry using fluorochrome-linked antibodies specific to each marker (BD Biosciences, San Jose, CA). Additionally, if an alteration in inflammatory status is indicated by the cytokine analysis, then the Th17 subset (CD4+, CCR6+, CD161+, ROR α +) will be evaluated. This pro-inflammatory subset has not been studied following supplementation or exercise and the results could provide for the first time information on whether alteration in Th17 t-cells accompanies improvement in immune status.

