- C. **Cytokine and Chemokines:** Immune responses are either predominated by pro-inflammatory Th1 cytokines (e.g. IFN- γ , TNF- α , IL-2, and IL-17) or anti-inflammatory Th2 cytokines (e.g. IL-10 and IL-4) and chemokines depending on the nature of the stimulus. However, arginine and glutamine may be able to limit the production of these factors [36]. Since aging is thought to increase basal cytokine levels and impair the cytokine response to exercise [60], the study will determine if 2-weeks of supplementation decreases baseline cytokine levels and increases the response to acute exercise. Cytokines and chemokines will be measured using the multiplex Luminex array system (Bio-Rad, Hercules, CA) and confirmed using high sensitivity enzyme linked immunosorbent assays (R&D Systems, Minneapolis, MN).
- D. **Immune Cell Proliferation:** In vitro models indicate that glutamine and arginine are important to immune cell proliferation [34;61]. Similarly, human trials of β -hydroxy- β -methylbutyrate, arginine, and glutamine have shown that monocytes, lymphocytes, and T-cells increase after treatment [27;46]. Proliferative capacity of lymphocytes also increases shortly after moderate exercise but the change is significant only in young and not older adults [58]. This study will determine if 2-weeks of supplementation increases the in vitro proliferative capacity of peripheral blood mononuclear cells at either baseline or after acute resistance exercise. After the in vivo effect of the supplement is determined, the results will be confirmed using the supplement or its individual ingredients to treat cells in vitro. Proliferation will be measured by flow cytometry based on uptake of a fluorescent dye (carboxyfluorescein succinimidyl ester) after treatment with phorbol ester and calcium ionophore as was used in Finding 5.

MUSCLE MEASURES

- E. **Macrophages:** Evidence from animal models indicates that arginine and glutamine metabolism is involved with macrophage activation that mediates inflammation or anti-inflammation and growth [35;37]. Our preliminary results indicate that the majority of macrophages residing in muscle perform the latter of these two functions, i.e. anti-inflammation and growth. However, muscle of

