older adults contains fewer macrophages and the numbers do not increase in response to acute exercise. The study will determine if 2-weeks of supplementation increases the number of macrophages present in muscle at baseline or in response to acute resistance exercise. Macrophages will be counted in muscle cross section by immunohistochemistry using antibodies to detect the CD163 marker (Cell Sciences, Canton, MA). Additional markers (CD68 and CD206) will be used to confirm the specificity of the CD163 marker to macrophages.

F. Cytokines and Growth Factors: Our preliminary results show that older muscle contains elevated basal levels of cytokines and diminished levels of growth factors. The effect of arginine and glutamine on cytokine expression is expected to be the same in tissue as it is systemically. The study will determine if 2-weeks of supplementation decreases baseline cytokine levels and increases the response to exercise. Since chronic inflammation is thought to dampen growth factor production [62], the study will determine if supplementation also increases growth factor levels at baseline and in response to exercise. IL1 β , IL10, and IGF1 are of primary interest though the other cytokines, and growth and remodeling factors *including MuRF and MAFbx* which will also be measured. Gene expression will be measured at the mRNA level using total RNA extracted from whole muscle by quantitative real-time PCR. Assays will utilize SYBR green chemistry and standard curves as was used in Findings 1-4 (Figures 2-5).

G. Nuclear Factor- κ B (NF κ B) and Phosphatidylinositol 3-Kinase Signaling (PI3K): Direct assessment of protein and protein activity in human muscle has proven difficult for cytokines and growth factors including IGF1, one of the most commonly studied regulators of muscle mass. For this reason, the study will evaluate muscle for cytokine (NF κ B) and growth factor (PI3K) activity by evaluating signal transduction pathways involved in regulation of muscle hypertrophy and atrophy [63]. The study will determine if 2-weeks of supplementation decreases NF κ B signaling and increases PI3K signaling at baseline and in response to exercise. NF κ B activity will be assessed by electrophoresis mobility shift assays to detect muscle nuclear protein binding to the NF κ B DNA site as used in Figure 9A or as follows for PI3K. PI3K activity will be assessed by Western Blot based phosphorylation assays (Millipore, Billerica, MA).

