STATISTICAL PLAN: The sample size (N=50) provides greater than 80% power for Aims 1-3 to detect mean differences between groups of 0.8 to 0.85 standard deviation (SD) units at a 5% level of significance. Power calculations were based on using a one-sided t-test to compare independent groups using data from our work and others [2;23;65] though non-parametric tests or transformations will be used as necessary for data containing outliers. There is no formal plan to adjust for multiple comparisons. However, multiple correlation analysis will be used to determine the correlation between endpoints and any possible inflation in the overall Type I error rate. This analysis will allow testing of the overall hypothesis that measures of immune function (Aim 1) will be positively correlated with adaptations to exercise (Aim 2) and retention of muscle strength, mass, and function after exercise training is halted (Aim 3). The hypotheses are stated for each aim and the time points for comparison are listed in Table 6.

Aim 1 Power: Aim 1 will determine if the supplement consumption for 2-weeks improves baseline measures of immune function or the immune responses to vaccination or acute exercise. The representative measures chosen to calculate power are change in muscle macrophage content after exercise (Finding 2) and change in CRP levels post-supplementation (Pilot Study Finding 1). Przybyla et al detected a 29% increase in CD163+ macrophages in young subjects after exercise but no change in older subjects [2]. Power for this aim is calculated to detect at least a 29% greater increase in macrophages in the supplement than the placebo group. Przybyla et al used a nonparametric test to lessen the effects of outliers. To be more conservative here, the calculations here dropped the most extreme high and low data values before estimating effect sizes. With that approach, the 29% increase corresponds to an effect size of 0.8 SD units (mean/SD = 0.128/0.159). Similar results were found using CRP data from Pilot Finding 1. The effect size for change in CRP is 0.85 SD units (mean/SD = 0.665/0.780 for log-transformed data). Having at least 20 subjects per group will provide 80% or greater power to detect a mean shift of 0.8-0.85 SD units at a significance level of 5% for the following Aim 1 hypotheses:

- a. The response to vaccination will be greater in the supplement than the placebo group. The change between times K and A (Table 6) will be compared between groups.

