- b. The resting ratio of CD4+ to CD8+ t-cells will increase in the supplement but not in the placebo group. The change between times G and C will be compared between groups.
- c. The change in t-cell subsets after acute exercise will be greater in the supplement than the placebo group. The change between times I and G will be compared to the change between times E and C for both groups.
- d. Resting cytokine levels will decrease in the supplement but not in the placebo group. Change will be compared between groups for blood (times G and C) and muscle (times H and D). *Similar results are predicted for the MuRF and MAFbx atrophy-related transcripts.*
- e. The increase in cytokine levels after acute exercise will be greater in the placebo group than the supplement group. For both groups, change between times I and G will be compared to the change

Table 6. Time points are lettered for clear reference by the stated hypotheses.	
BASELINE MEASURES (WEEKS 1-5)	
A.	Blood draw at study enrollment for measuring pre-vaccination antibody titers
B.	Assessment of muscle strength, mass, and function at baseline
C.	Blood drawn prior to acute exercise at baseline
D.	Muscle biopsy prior to acute exercise at baseline
E.	Blood drawn 1 hr after acute exercise at baseline
F.	Muscle biopsy 72 hrs after acute exercise at baseline
POST-SUPPLEMENT RUN-IN MEASURES (WEEK 8)	
G.	Blood drawn prior to acute exercise after 2-weeks of supplementation
H.	Muscle biopsy prior to acute exercise after 2-weeks of supplementation
I.	Blood drawn 1 hr after acute exercise after 2-weeks of supplementation
J.	Muscle biopsy 72 hrs after acute exercise after 2-weeks of supplementation
MEASURES DURING TRAINING PERIOD (WEEKS 9-20)	
K.	Blood draws at weeks 1 and 2 post-vaccination for measuring antibody response
POST-TRAINING MEASURES (WEEK 21)	
L.	Assessment of muscle strength, mass, and function after completion of training
M.	Muscle biopsy 72 hrs after final exercise bout of training
MEASURES DURING POST-TRAINING FOLLOW-UP (WEEKS 22-4)	
N.	Assessments of strength, mass, and function after 16 and 26 weeks of detraining

between E and C for blood, and for muscle the change between times J and H will be compared to the change between times F and D.

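### Aim 1 hypothesis e and the outcome section predict opposite directions for the cytokine response to acute exercise, and the plan does not say which one governs or whether the final test is one-sided

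*Combined protocol and SAP*

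**What the plan says.** The Statistical Plan makes the lettered statements under each aim the hypotheses to be tested: "The hypotheses are stated for each aim and the time points for comparison are listed in Table 6". For the cytokine response to acute exercise, Aim 1 hypothesis e states: "The increase in cytokine levels after acute exercise will be greater in the placebo group than the supplement group". It applies to blood (change I−G against change E−C) and to muscle (J−H against F−D).

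The section on laboratory outcomes frames the same measures the other way round:

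- Blood Measures C asks "if 2-weeks of supplementation decreases baseline cytokine levels and increases the response to acute exercise".
- Muscle Measures F says: "The study will determine if 2-weeks of supplementation decreases baseline cytokine levels and increases the response to exercise".

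The opening paragraph of the Statistical Plan mentions a one-sided t-test only as the basis of the power calculations, at a 5% level. It allows non-parametric tests or transformations where there are outliers. It does not say whether the final tests are one-sided or two-sided. The Study Outcomes paragraph lets an immune measure and its associated hypothesis change without this counting as a deviation.

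**The concern.** The measures, the stimulus and the two-week supplementation period are the same, but the predicted sign is opposite. Two directions for one comparison cannot both be the prediction. If nothing is settled before unblinding, a larger response on supplement fits the outcome section, a larger response on placebo fits hypothesis e, and either could be presented as confirming the plan.

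The direction also decides what a one-sided test can find. A one-sided test in the direction of hypothesis e has almost no chance of declaring the effect that Blood Measures C and Muscle Measures F ask about, although that effect could still be estimated with a confidence interval.

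**Working it through.** **1. Is the reversal confined to hypothesis e?** Set beside their outcome paragraphs, the other Aim 1 hypotheses agree in direction.

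- Resting cytokines: hypothesis d, "Resting cytokine levels will decrease in the supplement but not in the placebo group", matches the first half of the sentences in Blood Measures C and Muscle Measures F.
- T-cells: Blood Measures B asks whether supplementation "increases the CD4+ to CD8+ ratio or increases the response to acute exercise", and hypothesis c says: "The change in t-cell subsets after acute exercise will be greater in the supplement than the placebo group".
- Vaccination (a), resting T-cell ratio (b), proliferation (f), macrophages (g, h) and NFkB/PI3K signaling (i, j) also agree.

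Only the exercise cytokine response, one of ten hypotheses, is reversed.

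**2. Do the documents show which direction is meant?** They support both.

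- For a larger response on supplement: Blood Measures C says aging is thought to impair this response. Preliminary Studies, Finding 1 reports that older muscle "also lacks cytokine induction in response to acute resistance exercise" (muscle mRNA at 72 hours, so no direct evidence on blood at 1 hour).
- For a smaller response on supplement: Blood Measures C says arginine and glutamine may limit production of these factors. Muscle Measures G and hypothesis j expect lower NFkB signaling after exercise on supplement.

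**3. The plan's own power.** Inputs from the Statistical Plan: 20 per group, 5% level, one-sided t-test, 0.8 to 0.85 SD. For two equal groups of n, the t statistic has 2n−2 degrees of freedom and noncentrality d√(n/2). With n = 20, df = 38 and √(n/2) = 3.162. The critical values are 1.686 one-sided and 2.024 two-sided.

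| d (SD) | Noncentrality | One-sided power, matching direction | Two-sided power |
|---|---|---|---|
| 0.80 | 2.530 | 79.9% | 69.3% |
| 0.85 | 2.688 | 84.0% | 74.5% |

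The stated 80% reproduces one-sided only. The effect detectable with 80% power is 0.80 SD one-sided and 0.91 SD two-sided.

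**4. One-sided test in the direction of hypothesis e when the truth lies the other way.** The chance of rejection is P(T > 1.686) with noncentrality −d√10. The values of d are assumed, because the documents give no effect size or SD for the cytokine response.

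| True effect toward the outcome section (SD) | Chance of rejection |
|---|---|
| 0.3 | 0.5% |
| 0.5 | 0.07% |
| 0.8 | 0.002% |

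**5. Which SD?** Hypothesis e compares two exercise changes, one before and one after supplementation. The plan's 0.8 SD comes from a single exercise change in macrophages (0.128/0.159 = 0.805), and its 0.85 SD from the change in CRP (0.665/0.780 = 0.853). Suppose the two changes have equal variance and correlation r (an assumption; the documents give no r). The SD of their difference is then √(2(1−r)) times that of one change. An effect of 0.8 SD of a single change becomes 0.8/√2 = 0.57 SD of the contrast at r = 0, 0.8/√1.5 = 0.65 at r = 0.25 and 0.80 at r = 0.5. One-sided power is then about 54%, 65% and 80%.

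**The case against.** The strongest reply is that the detection problem is conditional. The plan ties one-sidedness to the power calculation alone, and the percentages in step 4 describe any one-sided test aimed the wrong way. A reader might infer that the final test of hypothesis e is one-sided and so blind to the outcome section's effect. The documents do not say that. Under a two-sided test that problem disappears and the conflicting predictions remain.

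A second reply is that the loss of power under a two-sided test is not particular to hypothesis e. This is correct: the same 20 per group, 0.8 SD and 5% level serve all three aims, so the drop from 80% to 69% is a plan-wide matter.

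A third is that the Study Outcomes paragraph allows hypotheses to change. It permits change but does not say which of two conflicting statements is current, so it does not resolve the conflict.

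A fourth is that one direction for all cytokines may be too coarse. This also stands. Blood Measures C separates pro- from anti-inflammatory cytokines, and Muscle Measures F names both IL1β and IL10 as of primary interest. But neither text assigns directions by class, so such a split does not reconcile them as written.

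It is also tempting to call hypothesis e a slip and the outcome section correct. The NFkB predictions and the suggested limiting effect of arginine and glutamine fit hypothesis e, so the documents do not support that reading.

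**Conclusion.** The contradiction is explicit and should be fixed before unblinding. It is confined in direction to one of ten Aim 1 hypotheses. It does not affect N=50 and creates no conflict of direction in the other hypotheses or in Aims 2 and 3.

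The certain consequence is that the prediction for this comparison is undefined. The near-zero chance of declaring an effect in the outcome section's direction follows only if the final test is one-sided as hypothesis e is worded. It also rests on 20 analysed per group, roughly normal data and assumed effects of 0.3 to 0.8 SD of the contrast tested.

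**What to change.** Before unblinding, reconcile Blood Measures C, Muscle Measures F and Aim 1 hypothesis e in one of two ways:

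- **State a direction.** Give the predicted direction and its reason, separately for pro- and anti-inflammatory cytokines where they differ. Use it in all three places and state that the final test is in that direction.
- **Test two-sided.** Where no direction can be justified, test hypothesis e two-sided at 5%.

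Any power quoted for hypothesis e should be in SD units of the difference between the two exercise changes. With 20 per group it is about 80% one-sided or 69% two-sided at 0.8 SD, and 80% two-sided at about 0.91 SD. The text should note that 0.8 to 0.85 SD comes from macrophage and CRP data.

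The cost is a few sentences and no change of sample size. The first option costs no power against the planned one-sided calculation. The second raises the detectable effect from about 0.80 to 0.91 SD.

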- f. The proliferative capacity of peripheral blood mononuclear cells will be greater in the supplement than the placebo group. The change between times G and C will be compared between groups. The change between times I and E will also be compared between groups.
- g. The resting number of muscle CD163+ macrophages will increase in the supplement but not in the placebo group. The change between times H and D will be compared between groups.
- h. The number of muscle CD163+ macrophages will increase after acute exercise in the supplement but not in the placebo group. The change between times J and H will be compared to change between times F and D for both groups.
- i. Resting NFkB activity will decrease and PI3K activity will increase in the supplement group but not in the placebo group. The change between time points H and D will be compared between groups.
- j. In response to acute exercise, NFkB activity will be lower and PI3K activity will be greater in the supplement group than in the placebo group. The change between times J and H will be compared to change between times F and D for both groups. *Responses similar to NFkB are predicted for FOXO1, and responses similar to PI3K are expected for STAT3, AKT, P38 MAPK, and ERK 1 and 2.*

Aim 2 Power: Aim 2 will determine whether supplement consumption increases muscle adaptation to 12-weeks of resistance training. The representative response measure for this objective is post-training percent increase in muscle strength. In a similar study, Trappe et al sought to improve strength gain by resistance training plus drug treatment. The drug treatment group gained significantly more strength by 25.1% than the group receiving placebo (26.4% vs. 21.1%, $P<0.05$) [23]. The previous findings presented here (Finding 4) indicate that older subjects completing a 12-week training program but not taking supplements will experience an average strength gain of $25 \pm 8\%$. If treatment with the proposed supplement improves strength similarly to the Trappe drug treatment, subjects in the supplement group will improve strength by an average of 31% (i.e., 25.1% greater than those of the placebo group). This translates to an approximate effect size of 0.8 SD units ($0.25*0.251/0.08$) if variances are pooled for the groups compared. With 20 subjects per group, there will be 80% power to detect a mean shift of 0.8 SD units using a significance level of 5% for the Aim 2 hypotheses:

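### Aim 1 hypotheses c, e, h and j are the only ones whose comparison sentence does not name a between-arm test, and h as worded could be declared from two within-arm tests

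*Combined protocol and SAP*

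**What the plan says.** The Statistical Plan lists ten Aim 1 hypotheses, a to j, each with a prediction and a comparison sentence that refers to the lettered time points of Table 6. Four of them concern the response to a single exercise bout, measured before and again after two weeks of supplementation.

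- **c (T-cell subsets).** Prediction: "The change in t-cell subsets after acute exercise will be greater in the supplement than the placebo group". Comparison: "The change between times I and G will be compared to the change between times E and C for both groups".
- **e (cytokines).** Prediction: "The increase in cytokine levels after acute exercise will be greater in the placebo group than the supplement group". Comparison: "For both groups, change between times I and G will be compared to the change" from C to E in blood, with J-H set against F-D in muscle.
- **h (macrophages).** Prediction: "The number of muscle CD163+ macrophages will increase after acute exercise in the supplement but not in the placebo group". Comparison: "The change between times J and H will be compared to change between times F and D for both groups".
- **j (signalling).** Prediction: "NFkB activity will be lower and PI3K activity will be greater in the supplement group than in the placebo group". The comparison sentence is the same as in h.

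Hypotheses a, b, d, f, g and i, and all those of Aims 2 and 3, use a different form. Hypothesis g, on resting macrophages, is typical: "The change between times H and D will be compared between groups".

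The opening of the Statistical Plan bases power on a one-sided t-test of independent groups. The Aim 1 Power paragraph applies that basis to the whole list of Aim 1 hypotheses. The Methods part of the Abstract likewise describes the hypotheses on these measures as tested for a difference in means between the supplement and placebo groups.

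**The concern.** In c, e, h and j the two quantities being compared are the post-supplement and the pre-supplement exercise response. The arms are named as the places where the comparison is made, not as the things compared. An analyst following the sentence literally could run a paired test in each arm and stop there.

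Significance in one arm and non-significance in the other is not a test of a difference between arms. A shift common to both arms can push one arm over the threshold and leave the other just short of it.

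The design leaves room for such a shift. The second bout repeats the same exercises about three weeks after the first (weeks 5 and 8 of the study timeline). Under the Muscle Biopsy section, pre-exercise samples come from the dominant leg and post-exercise samples from the other, so each leg is sampled again at the second bout. A between-arm test removes any common order or repeat-sampling effect; two within-arm tests do not.

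The exercise response of CD163+ macrophages, the endpoint of h, is also one of the two measures chosen to represent Aim 1 in the power calculation, and there is no formal multiplicity adjustment.

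**Working it through.** **1. Reproduce the plan's power figure.** Inputs from the Statistical Plan: 20 per arm, one-sided 5%, and effect sizes of 0.128/0.159 = 0.805 SD (macrophages) and 0.665/0.780 = 0.853 SD (CRP), rounded there to 0.8 and 0.85. For a two-sample t-test, the noncentrality is d × √(n/2) on 38 degrees of freedom.

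- d = 0.80: noncentrality 0.80 × √10 = 2.53, power 79.9%.
- d = 0.85: power 84.0%.

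The stated 80% is reproduced, and 40/(1 - 0.20) = 50 matches the planned N. The plan's power is therefore that of a between-arm comparison.

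**2. The within-arm rule when the arms do not differ.** Let δ be the true shift, the same in both arms, in SD units of the within-subject difference (J-H)-(F-D). A positive δ is in the predicted direction. Let p be the chance that one arm's one-sided paired t-test is significant: n = 20, 19 degrees of freedom, noncentrality δ × √20. The arms are independent, so

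P(supplement significant, placebo not) = p × (1 - p).

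| Shared shift δ | p | p × (1 - p) |
|---|---|---|
| -0.4 | 0.0004 | 0.04% |
| -0.2 | 0.0061 | 0.6% |
| 0 | 0.0500 | 4.75% |
| 0.2 | 0.2171 | 17.0% |
| 0.3 | 0.3628 | 23.1% |
| 0.38 | 0.4975 | 25.0% (maximum) |
| 0.4 | 0.5318 | 24.9% |
| 0.6 | 0.8266 | 14.3% |

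Simulation (100,000 trials each at δ = 0, 0.2 and 0.38) gave 4.7%, 17.0% and 25.1%. In the same trials a between-arm t-test of the difference was positive in 4.9% to 5.0%. Between 58% and 82% of the supplement-only findings had a non-significant between-arm test.

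**3. Which between-arm test.** If a between-arm test is intended, the plan does not say whether it uses the raw difference of the two responses or an adjusted analysis. The power section describes the macrophage effect as a change after exercise. Suppose that 0.8 SD is in units of one such change, that both changes have the same SD, and that they correlate at ρ within a subject (not given in the documents). Then:

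- raw double difference: effective effect 0.8/√(2(1-ρ)), 38 degrees of freedom;
- ANCOVA on the pre-supplement response: effective effect 0.8/√(1-ρ²), 37 degrees of freedom.

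| ρ | Double difference: effect, power | ANCOVA: effect, power |
|---|---|---|
| 0 | 0.566, 54% | 0.800, 80% |
| 0.25 | 0.653, 65% | 0.826, 82% |
| 0.5 | 0.800, 80% | 0.924, 89% |
| 0.75 | 1.131, 97% | 1.209, 98% |

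The ANCOVA is at least as powerful at every ρ shown.

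**The case against.** A reader might infer that the plan tests these four hypotheses only within arms and would declare them with no between-arm test at all. The documents do not support that.

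- The Abstract and the power section both frame the hypotheses as a difference in means between supplement and placebo, and the power section makes no exception for c, e, h and j.
- The power target for macrophages is an increase at least 29% greater in the supplement arm than in the placebo arm, which is the endpoint of h stated as an arm difference.
- Hypotheses c, e and j predict arm differences outright, and two separate paired tests could not answer them.
- Hypotheses b, d, g and i also predict a change in one arm but not in the other, and then specify a between-group comparison. The authors may use that phrasing as shorthand.
- The comparison sentence in c, e, h and j can be read as defining each subject's difference of changes, computed in both arms and then compared.

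All of this stands, and it makes a between-arm test the likely intention. It does not settle the matter, because the basis of a power calculation is not an analysis specification. The hypothesis sentences are where the plan defines its contrasts.

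A reader might also take 17% to 25% as the false-positive rate of the plan. That does not stand. Those figures need a shared shift of 0.2 to 0.4 SD in the predicted direction, and no document gives one. At zero shift there is no inflation. If the second bout provokes a weaker response because it is less unaccustomed, the shift in h runs against the prediction and the rule fires less often than 5%. Blunting could favour the predictions for cytokines in e and NFkB in j, but those are already worded as arm differences.

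Finally, ANCOVA is an efficiency choice. A between-arm t-test on the difference of changes would also be valid.

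**Conclusion.** The point holds as an ambiguity that should be closed. Four of the Aim 1 hypotheses lack the between-group wording that every other hypothesis has. For three of them the prediction itself calls for an arm comparison. For h, the text as written could be satisfied by two within-arm tests.

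Under that reading of h, with 20 per arm at one-sided 5% and no true arm difference, a false supplement-only finding occurs in 4.75% of trials with no shared shift, 17% at 0.2 SD, at most 25% near 0.38 SD, and under 1% at -0.2 SD or worse. A between-arm test stays at 5% throughout. The size of the problem depends on an assumed shift whose magnitude and direction the documents do not give. The power gain from ANCOVA likewise depends on an unstated correlation and on reading 0.8 SD as the effect on a single exercise change.

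**What to change.** 1. In c, e, h and j, replace the comparison sentence with: the post-supplement exercise response (I-G in blood, J-H in muscle) will be compared between groups by ANCOVA, with the pre-supplement response (E-C in blood, F-D in muscle) as covariate.
2. Reword the prediction in h as a greater post-exercise increase in CD163+ macrophages in the supplement group than in the placebo group.
3. State that any before/after test within an arm is descriptive and will not support a claim of a supplement effect.

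The cost is a change of wording in the Statistical Plan. All the measurements are already scheduled, and neither the sample size nor any procedure changes. It should be made before unblinding.
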